Dondzila et al. found that older adults who considered themselves physically active actually walk more than those who do not rate themselves as physically active.¹⁴ The Physical Activity Guidelines for Americans recommend 150 minutes each week of moderate intensity aerobic activity or 75 minutes each week of vigorous intensity aerobic activity.¹⁵ The Centers for Disease Control and Prevention (CDC) reported that “1 out of 5 adults (21%) meet the 2008 Physical Activity Guidelines”.¹⁶ For the older adults, the threshold amount of physical activity associated with better physical health is >8000 steps/day and/or >20min/day at an intensity of >3 Metabolic Equivalent (METS) and for better mental health, >4000 steps/day and/or >5min/day at >3METS.¹⁷ Men aged 65-69 years performed the highest steps per day (>9,126 steps/day) and women aged 85+years were in the lowest category of steps per day (<276 steps/day).¹⁸

Currently, 10,000 steps per day is a widely promoted dosage-based walking program. In older adults, increased lower and upper body strength, endurance, lower body flexibility, and agility/balance were significantly and positively associated with walking 6500 or more steps per day.¹⁹ Low-activity, non-depressed older adults were able to maintain and/or improve their mental health.²⁰ High volume of steps led to an increase in the Timed Up and Go (TUG) score, 30-second leg lifts and 2-minute walking distance.²¹

Because of the detrimental effects of sedentary lifestyle, interventions to increase physical activity are a public health priority.²² There are many instruments available to track the amount of physical activity of an individual subjectively and objectively.²³ A self-report physical activity questionnaire is a cost-effective method to obtain physical activity data. The International Physical Activity Questionnaire (IPAQ) is the most commonly used physical activity questionnaire worldwide. It has two versions, a 31-item long form and the nine-item short form. The short form records the amount of time spent in sitting, walking, moderate- and vigorous-intensity activities in the last 7 days.²⁴

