The VRWP group will have VR with an instruction to increase their number of steps daily to at least 3,000 steps using the pedometer (VR plus walking plus pedometer group). They will receive pedometers (Fitbit Zip), instructions on how to use the pedometer, step log forms, with home instruction handout to walk more at least more than ten minutes at a time. This group will be instructed to wear a pedometer on or below the waist such as belt, waistband, or in trousers' pocket, during waking hours, all day, except for bathing or swimming. A clip designed to keep the Fitbit Zip clipped to the clothing will be provided. There is no charging time. Fitbit Zip uses a replaceable watch battery that can last up to 6 months. The participants will record on their activity log the number of steps shown on the step display at the end of the day. The Fitbit Zip will be device inclusive. Subjects will not be given instruction to program their information or synchronize their Fitbit Zip with an application software on a smart phone, tablet, or any computer device. The daily step log form will be given to the research staff every visit for recording. The research staff will encourage their participants to increase their daily steps at least 10% until they achieve at least 3,000 steps daily. The older adults in the group will be trained on how to use the pedometers before they take them home, and will have the opportunity to review this instruction with the research staff on consecutive visits if needed. There may be cost associated with the study in case of lost or malfunction from using the pedometer due to the subject will be encouraged but not required to replace the pedometer. The subject will continue to be the VRWP group and this situation will be reported in the discussion of results.

The VRW group will receive VR and a time-based instruction to walk more daily at least 10 minutes at a time (VR plus walking no pedometer group). This group will be instructed on the benefits of walking (similar to the first group) but will not be given the pedometer. They will have home instruction handouts to walk more at least more than ten minutes at a time and a walking log sheet. The research staff will instruct their participants to increase their daily time at least 10% until they achieve at least 30 minutes of walking exercise daily. The walking log sheet form will be given to the research staff by the participant every visit for recording.

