The principal investigator may share the research data with accreditation organizations and regulatory agencies, dissertation committee, and publications, medical meetings, or scientific journals for the purposes of completing the research study, and analyzing and evaluating the results. Individual patients (subjects) will not be identified during data sharing, and a research number will be used instead during the data sharing process, unless necessary to carry out the research study or required by law.

Sample Size Determination

A priori power analysis predicting a large effect size ($F=.25$) determined that a total of 54 subjects (18 in each group), who met the inclusion and exclusion criteria will be needed, with alpha at the conventional value of .05 to achieve a .80 power, that includes an assumption of a dropout rate of 10% .

Statistical Analysis Plan

The results will be presented through the following tables with supporting explanations:

- Clinical and sociodemographic characteristics of participants by group at baseline.
- Comparisons of TUG, DGI, mCTSIB and DHI between the three intervention groups on admission and discharge.
- Comparisons of self-reported walking activity (walking MET-min/week) and total self-reported energy expenditure (total physical activity MET-min/week) as determined from the IPAQ short form on admission, discharge and four-week follow-up between the three intervention groups
- Comparisons of averages of compliance to step log recording and compliance rate for meeting step goal between the VRWP and VRW groups. Compliance is defined as low (<33%), moderate (33%-75%) and high (>75%) based on the step log or walking log. This grading of compliance was used by Hall and colleagues in their research on efficacy of gaze stability exercises in older adults with dizziness.⁵³
- Comparisons of total number of visits and length of interventions in weeks between the three intervention group.
- Intraclass Correlation Coefficients for the Timed Up and Go test-retest reliability
- Result of stepwise linear regression analysis for TUG, DGI, mCTSIB and DHI

All interval and ratio data will be tested for normality prior to undertaking the data analysis. Descriptive statistics will be used to describe the characteristics of the sample and compare the three groups at baseline. This will include Analysis of Variance (ANOVA) for parametric and Chi Square for nonparametric sociodemographic and clinical data.

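### VRWP and VRW differ in walking goal and log as well as in the pedometer, so Objective 2 can be answered for the package but not for the pedometer alone

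*Combined protocol and SAP*

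**What the plan says.** The abbreviation list and the Randomization section name the arms additively: rehabilitation plus walking plus pedometer (VRWP), rehabilitation plus walking instruction only (VRW), and usual rehabilitation (VR). Study Objectives sets the second purpose as finding out whether pedometers raise adherence. It measures this by IPAQ Walking and Total scores and describes the comparator only as patients told to walk who have no pedometer. Data Analysis, Objective 2, repeats the question.

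The Randomization section then describes the two walking arms. VRWP participants get "an instruction to increase their number of steps daily to at least 3,000 steps using the pedometer". They wear the device throughout waking hours and log "the number of steps shown on the step display at the end of the day". VRW participants get a time-based instruction and a walking log sheet, and staff tell them to "increase their daily time at least 10% until they achieve at least 30 minutes of walking exercise daily".

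For IPAQ, Data Analysis names a Kruskal-Wallis test across the three groups. The Statistical Analysis Plan also lists a comparison of the "compliance rate for meeting step goal between the VRWP and VRW groups", with compliance graded from whichever log the arm keeps.

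**The concern.** A reader who sees the labels and the objective will assume that the device is the only difference between VRWP and VRW. If so, a difference in IPAQ change could be credited to the pedometer, and a null result could be taken as evidence against it. In fact the goal and the log change with the device. A difference could come from any of these elements, and a null result could hide effects that cancel. The Publication Plan anticipates a separate paper for this objective, and clinics deciding whether to supply devices would read its answer. Nothing in the documents limits that answer to the package.

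**Working it through.** The plan gives no figure on this point to reproduce. The check sets the two prescriptions side by side and asks what the contrast identifies.

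**Step 1. The arms, from the Randomization section.**

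| Element | VRWP | VRW |
|---|---|---|
| Vestibular rehabilitation | yes | yes |
| Advice on benefits, ten-minute handout | yes | yes |
| Increments of at least 10% | yes | yes |
| Log handed in at each visit | yes | yes |
| Pedometer and training in its use | yes | no |
| Goal | at least 3,000 steps over the whole day | at least 30 minutes of walking exercise |
| Type of log | steps | walking |

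The last three rows differ together. Table 1 refers to steps in the VRW increment, but its VRW target is still 30 minutes and that arm has no counter.

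**Step 2. What the contrast identifies.** Write m(d, g) for mean IPAQ change with device d (1 or 0) and goal g (S for steps, T for time), each goal taken with its own log. The trial observes m(1, S) in VRWP and m(0, T) in VRW. Then

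m(1, S) − m(0, T) = [m(1, S) − m(1, T)] + [m(1, T) − m(0, T)].

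The first bracket is the effect of goal and log among pedometer users. The second is the effect of the device at a fixed goal. No arm supplies m(1, T), so there is one observed quantity and two unknowns. Any device effect is compatible with any observed difference, including zero. Splitting the effect the other way needs m(0, S), which is also absent. The VR arm does not help, because it has neither a device nor a walking goal.

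**Step 3. Are the goals equivalent, or ordered?** No section equates them. Converting steps to minutes needs a cadence, which the documents do not give, so I assume 60 to 120 steps per minute. Minutes = 3,000 / cadence. IPAQ walking MET-minutes per week = minutes × 7 × 3.3, with the 3.3 weight taken from Study Outcome Measures. The VRW goal at its floor is 30 × 7 × 3.3 = 693.

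| Assumed cadence (steps/min) | 3,000 steps in minutes | MET-min/week | Minus 693 |
|---|---|---|---|
| 60 | 50 | 1,155 | +462 |
| 80 | 37.5 | 866.25 | +173.25 |
| 100 | 30 | 693 | 0 |
| 120 | 25 | 577.5 | −115.5 |

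These figures compare the two floors and treat every step as walking exercise. They are not estimates of bias. The sign changes within the range.

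An individual can also meet either goal without the other. Someone with 3,000 ordinary steps and no walking exercise meets only the VRWP goal. Someone who walks 30 minutes at 60 steps per minute takes 1,800 steps and, with fewer than 1,200 other steps that day, meets only the VRW goal.

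So the goals are different prescriptions, and the documents do not show which is the more demanding.

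**The case against.** The strongest defence is that the documents nowhere claim an effect of the pedometer alone. The trial is called pragmatic, the VRW instruction is openly described as time-based, and Table 1 sets out both programmes. People without a counter cannot readily follow a step goal, so a step goal and step log are how a pedometer is ordinarily used, and the objective can be read as asking about pedometer-guided walking. There is also no Objective 2 conclusion in the documents to fault. Much of this stands: the package comparison is valid and useful, and the point is one of wording. What does not stand is that readers will see this unaided. The labels are additive, the objective describes the comparator only by its lack of a pedometer, and a pedometer arm with a time goal was possible.

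Three stronger readings are tempting, and the documents do not support them.

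- *The VRW goal is the harder one.* The Background links better physical health to ">8000 steps/day and/or >20min/day at an intensity of >3 Metabolic Equivalent (METS" and better mental health to ">4000 steps/day and/or >5min/day at >3METS". Against these, 3,000 steps is 3,000/8,000 = 37.5% and 3,000/4,000 = 75%, while 30 minutes is 30/20 = 1.5 times and 30/5 = 6 times. But these are associations, not conversions. The minute thresholds require an intensity above 3 METs, VRW's pace is unspecified, and the 3.3 weight is a scoring constant.
- *Many VRWP participants would meet 3,000 steps before starting.* The Background reports "Men aged 65-69 years performed the highest steps per day (>9,126 steps/day", against fewer than 276 in the group at the other extreme, the oldest women. These are bounds for extreme age-sex groups, not values for older adults referred for dizziness.
- *The compliance comparison is meaningless because VRW cannot count steps.* The Statistical Analysis Plan says that compliance is graded from the step log or the walking log, so each arm can be judged on its own record. The term *step goal* is loose shorthand.

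**Conclusion.** The concern holds as a limit on attribution, and its severity is minor. VRWP versus VRW estimates the effect of one walking package against another. It cannot isolate the device, whether the IPAQ result is positive or null. This follows from the arm descriptions alone and does not depend on the assumed cadences, which serve only to show that the goals cannot be ranked. No size or direction of bias and no loss of power can be derived, and none is claimed. A reader might infer that the randomised comparison is flawed; it is not. Separately, the stated IPAQ test compares three groups at once, so a significant result would not by itself show that VRWP and VRW differ.

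**What to change.** Leave Objective 2 as it stands and make three changes.

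1. Define the VRWP versus VRW contrast, and word its conclusion, as *pedometer with a 3,000-step goal versus time-based walking instruction with a 30-minute goal*. Do not attribute an IPAQ difference, or its absence, to the device itself.
2. Base that conclusion on a pairwise VRWP versus VRW comparison of IPAQ change, using data already collected. A two-group rank test would match the nonparametric approach in Data Analysis. Because no such IPAQ test is stated there, report it as an addition to the plan.
3. Describe the compliance comparison as each arm's compliance with its own goal on its own log.

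The cost is some rewording, one small extra analysis and a narrower conclusion about pedometers. No further patients, visits or data are needed, and all of it can be done after data collection.

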The VR (control) group will follow the conventional VR physical therapy without the encouragement of walking and without specification of walking in the home exercise program.

The use of an assistive device can be recommended for any subject in any group by the research staff to maximize safety. The patient may need to purchase the assistive device.

Participants who do not belong to the intervention group with pedometer will receive a pedometer after they completed the study. They will receive instructions on how to use the pedometer prior or on the day of their last visit.

Study Visits

For the experimental design that will be conducted at Florida Hospital locations, the following data will be collected as standard of care by the physical therapist during initial evaluation, and if more time is needed, during the first follow-up physical therapy appointment: mCTSIB, TUG, DGI, DHI, age, gender, body mass index, home situation, Functional Comorbidity Index (FCI) total, ability to drive, medications and insurance type. After the subject signs the informed consent, the study coordinator will be notified by the research staff to conduct a retrospective chart review on the physical therapy initial evaluation and first follow-up visit, if applicable, of the subject. The study coordinator will extract the following baseline measurements from the subject's medical record: DGI, mCTSIB, DHI, TUG and socio-demographic data that include age, gender, body mass index, home situation (lives alone or with social support), Functional Comorbidity Index (FCI) total, ability to drive (able or unable), medications for vertigo and insurance type (Medicare/Non-medicare). Based on the retrospective chart review, the study coordinator will determine if the subject is eligible to participate in the study.

Visit 1: Once the study coordinator determined that the subject is eligible to participate in the study, the subject will be assigned a research number and will be randomized into one of the three intervention groups. The research staff can initiate or continue the VR program. For the test-retest reliability of the TUG test, there will be one practice trial followed by two final performances that will be included in the data analysis. The subject will also be asked to complete the IPAQ-short form questionnaire. The test-retest reliability of TUG and the IPAQ-short form questionnaire are for research purposes only.

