Visit 2: The research staff can initiate the research intervention according to the intervention group.

Visit 3 to visit prior to discharge: The research staff can continue the VR and intervention according to the intervention group.

Discharge or last visit: All outcome measures (DGI, TUG, mCTSIB, DHI and IPAQ) will be reassessed. Discharge scores for DGI, TUG, mCTSIB and DHI are standard of care, while IPAQ is for research purposes only. The total number of visits and length of

interventions (in weeks) for every participant will be recorded as secondary outcome measures. These research data will be forwarded to the study coordinator, and will be stored in a locked cabinet and password protected Florida Hospital computer.

Four-weeks after discharge: The study coordinator will conduct a follow up phone call to all subjects four weeks after discharge summary is completed to obtain the level of physical activity using the IPAQ short form questionnaire. This is for research purposes only. A follow-up on a subject will be discontinued if a subject is not reached after three attempts of follow-up phone call made on three different days between 30 and 45 days. Data analysis will commence once all the data from 54 subjects are collected.

Table 1. Summary of Interventions for VRWP, VRW and VR Groups.

VRWP (n=18)	VRW (n=18)	VR (n=18)

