
 Visit 1: Test-retest of TUG. Subject will complete the IPAQ-short form. Randomization. Initiate or continue with VR. Visit 2: initiate HEP on walking with pedometer. Patients will be given a pedometer and instruction on how to use it. Participants will be encouraged to increase their daily steps at least 10% until they achieve at least 3,000 steps daily. Visit 3 to visit prior to discharge: Continue with VR. Continue with instruction on how to use the Fitbit Zip pedometer as needed. Treating therapist will monitor and keep a record of the 	
 Visit 1: Test-retest of TUG. Subject will complete the IPAQ-short form. Randomization. Initiate or continue with VR. Visit 2: Initiate HEP on time-based walking. Patients will be instructed to walk at least 10 minutes at a time. Participants will be encouraged to increase their daily steps at least 10% until they achieve at least 30 minutes of walking exercise daily. Visit 3 to visit prior to discharge: Continue with VR. Treating therapist will monitor and keep a record of the patient's daily step log form every visit. Discharge day: mCTSIB, DGI, 	
 Visit 1: Test-retest of TUG. Subject will complete the IPAQ-short form. Randomization. Initiate or Continue with VR. Visit 2 to Visit prior to discharge: Continue with VR, without the encouragement of walking and without specification of walking in the home exercise program. Discharge day: mCTSIB, DGI, DHI, TUG and IPAQ short form, total number of visits and length of intervention (in weeks). Four-week follow-up: phone call for IPAQ short form Pedometers will be mailed to participants as a reward for

patient's daily step log form every visit.
 
 • Discharge day: mCTSIB, DGI, DHI, TUG and IPAQ short form, total number of visits and length of intervention (in weeks) • Four-week follow-up: phone call for IPAQ short form 	
DHI, TUG and IPAQ short form, total number of visits and length of intervention (in weeks).
 
 • Four-week follow-up: phone call for IPAQ short form • Pedometers will be mailed to participants as a reward for participation. 	
participation.

---	--	-----------------------

Study Duration

TIMELINE

Month	Task	2017 Dec	2018 Jan	Feb	Mar	Apr	May	June
IRB Submission		X						
Protocol Set		X						
Completion of Training Requirements by Research Personnel		X						

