Subjects may withdraw or take away the permission to use and disclose their health information for any reasons at any time. This can be done by sending a written notice to the PI. Information that has already been gathered may still be used or given to others, however no new health information that might identify the subject will be gathered after the subject withdraw from the study.

Data Collection and Follow-up for Withdrawn Subjects

Patients who request withdrawal or who are withdrawn by the PI from the study will have their information that has already been gathered and shared in the research database. These data will be included in the data analysis. The percentage of patients withdrawing will be calculated.

Adverse Event Reporting

At each therapy visit of the subject, the research staff/treating therapist will seek information if there is any adverse event caused by taking part in the study. In the event of a research-related injury, the subject should report this in person or by phone to the research staff/treating therapist and PI. All adverse events will be reported to Florida Hospital's IRB and Nova Southeastern University's IRB following their respective policies for reporting adverse events.

Safety Monitoring Plan

Safety Monitoring
N/A

Data and Safety Monitoring Board (DSMB) or Equivalent
N/A

Ethical Considerations

Subjects in the VRW and VR group will receive a pedometer after they completed the study.

Sharing of Results with Subjects

Results of the study that are part of standard physical therapy will be shared with subjects and referring physicians. Letters will be sent to all participants that contain the results of the research once the research is completed.

Funding Source

Application for funding will be done through the Adventist University in January 2018. The principal investigator is currently requesting managers to allow the allocation of her Continuing Education budget for 2018 for this study.

Subject Stipends or Payments

The pedometer will be donated to the 54 participants, who met the inclusion and exclusion criteria and randomized into one of the three treatment groups, as a reward for participating in the research study and for them to perpetuate their physical activity.

Publication Plan

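### The Visit 1 text and Table 1 give opposite orders for the baseline IPAQ and randomisation, and nothing withholds the assignment until the IPAQ is complete

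*Combined protocol and SAP*

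**What the plan says.** Study Objectives makes the IPAQ walking and total scores the measure for the pedometer question, at admission, discharge and four weeks later, with the walking-instruction arm (VRW) as comparator.

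**Order at Visit 1.** Under Study Visits, the Visit 1 paragraph begins by saying that, once eligible, "the subject will be assigned a research number and will be randomized into one of the three intervention groups". It then allows VR to start or continue, describes the TUG trials, and only after that adds: "The subject will also be asked to complete the IPAQ-short form questionnaire". Table 1 has the TUG first and then, in each of its three columns, "Subject will complete the IPAQ-short form. Randomization. Initiate or continue with VR". The arm-specific programme comes later: "Visit 2: The research staff can initiate the research intervention according to the intervention group".

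**Pedometer teaching for the comparators.** The Randomization section says of patients outside the pedometer arm: "They will receive instructions on how to use the pedometer prior or on the day of their last visit". The device itself comes later. Ethical Considerations says "Subjects in the VRW and VR group will receive a pedometer after they completed the study". In the VRW and VR columns of Table 1, the entry after the four-week call is "Pedometers will be mailed to participants as a reward for participation". Patients in VRWP, by contrast, "will be trained on how to use the pedometers before they take them home".

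**Who collects the IPAQ.** Under Resources Available, the treating therapists collect it in clinic and also deliver the interventions. The study coordinator, who assigns patients from the master list, makes the four-week call.

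**The concern.** The IPAQ is a self-report, and here nobody who answers it or collects it is masked. A patient who already knows the assignment may describe the past week differently, for example by understating walking before a walking programme. A therapist who knows the arm may prompt differently. A baseline shifted in this way carries into every change score built on it. The two accounts of Visit 1 differ, so therapists at the two sites could follow different orders and each comply with the document.

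The second, lesser matter is that comparators are taught to use the device under test before the last IPAQ is taken. If that teaching alters walking or its reporting, the four-week comparison of VRWP with VRW is no longer quite pedometer against no pedometer.

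**Working it through.** No figure in the plan bears on this point, and neither change affects the sample size of 54. The check is of order and timing.

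**1. Order of steps at Visit 1**

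| Source | Listed order |
|---|---|
| Study Visits, Visit 1 | randomisation, VR, TUG trials, IPAQ |
| Table 1, all three columns | TUG trials, IPAQ, randomisation, VR |

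The Visit 1 paragraph gives a sequence and not an express rule, but the two sequences are opposite on the step that matters. The Randomization section has the coordinator assign the patient once eligibility is confirmed and does not mention the IPAQ. No section says when the assignment is disclosed.

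**2. What an early assignment could affect.** The Background says the short form asks about the last 7 days. The walking programme starts at Visit 2. The week recalled at Visit 1 therefore precedes any arm-specific treatment under either order. VR may already be under way, but before assignment it does not differ by arm. Only the reporting can be affected.

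**3. Where the baseline enters.** Data Analysis, Objective 2, classifies change over three intervals: pretest to posttest, posttest to four weeks, and pretest to four weeks. The baseline IPAQ enters the first and third (2 of 3). The four-week IPAQ enters the second and third (2 of 3).

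**4. Timing of comparator teaching.** Let day 0 be the last visit, which Study Visits equates with discharge, and assume the discharge summary is completed that day.

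- Discharge IPAQ: recall covers the 7 days before day 0. Teaching on day 0 cannot change that walking; teaching before the last visit could.
- Four-week IPAQ, call on day 28: recall starts on day 28 − 7 = 21, wholly after the teaching.
- Last permitted call attempt, day 45: recall starts on day 45 − 7 = 38, again wholly after.
- Device: listed for mailing after the call, so no study pedometer is in hand during either window.

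A later discharge summary moves the calls later and leaves these conclusions unchanged.

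**5. Reach.** The teaching rule covers 18 VRW + 18 VR = 36 of 54 patients (36/54 = 67%), including all 18 in the named comparator arm. This is a headcount and not a measure of bias.

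**The case against.** The case for leaving the plan alone is reasonable. Table 1 already has the preferred order, and assignment from a list held by the coordinator need not mean that the patient is told before answering. On the teaching, nothing in the documents shows that explaining a device the patient does not have changes walking. VRW patients already receive the benefits talk, a handout, a log and a rising goal. The last visit is the last planned face-to-face contact, so teaching people aged 65 or older there has an obvious practical reason. Adherence is also compared through log compliance during treatment, which does not depend on the four-week call.

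Most of this stands, and it keeps the point small. It does not remove the conflict between the two accounts of Visit 1 or supply the missing disclosure rule.

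Three stronger readings are tempting and are not supported:

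- *That baseline walking is already contaminated by treatment.* The Visit 2 start and the 7-day recall rule this out.
- *That early teaching can only shrink the VRWP contrast.* Dilution is the likelier direction, but a patient expecting a pedometer might also postpone walking until it arrives. The documents do not settle the net direction.
- *That the two edits would secure the IPAQ.* It remains an unmasked self-report whatever the order. The edits remove two avoidable routes to bias and no more.

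**Conclusion.** The point holds as an internal contradiction plus a missing rule on when the assignment is released. The consequence is limited to post-assignment colouring of a self-report that enters two of the three Objective 2 change intervals. The documents give no basis for a size; it is probably small.

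The comparator teaching is secondary. It always precedes the four-week IPAQ, and it precedes the discharge IPAQ only if given before that questionnaire is completed. Any contamination is unquantified, limited by the absence of a study device, and most likely towards no difference.

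This rests on reading the last visit as discharge, as Study Visits does, and on pedometers being mailed after the four-week call, as Table 1 lists. The Data Analysis section is written in the past tense. If data collection is complete, the text changes can no longer act on the data and only reporting remains.

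**What to change.** 1. **Reconcile Visit 1 (free).** Amend the Visit 1 paragraph to the Table 1 order and add: *The TUG trials and the IPAQ short form are completed before the assignment is released to the patient and the treating therapist.* This needs no extra visit, staff or data.

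2. **Move comparator teaching (optional, low cost).** Replace the teaching sentence with: *VRW and VR participants receive pedometer instructions only after the four-week IPAQ is obtained or the last call attempt has failed, as a printed sheet enclosed with the mailed pedometer.* Shipping to these arms is already a budget line, so the addition is one sheet per parcel, at most 36. Print is simpler than teaching at the end of the call, because Resources Available lists Fitbit Zip instruction for the treating therapists and not expressly for the coordinator who calls. The cost is the loss of face-to-face teaching. As with any modification, both edits need approval before use under the multi-site communication plan.

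3. **If data collection is complete.** Report the order actually followed at Visit 1, when comparators were taught, and that patients, the therapists collecting the clinic IPAQ and the four-week caller knew the arm, as limitations of Objective 2. The statement about unmasked collection belongs in the report in any case.
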